# **Statement of Intent and Compliance**

This trial will be conducted in compliance with the protocol outlined herein. This document is a protocol for a clinical research trial. The trial will be conducted in compliance with all stipulations of this protocol, the conditions of ethics committee approval, the NHMRC National Statement on Ethical Conduct in Human Research (2007) and the Note for Guidance on Good Clinical Practice (CPMP/ICH/135/95).

# **Summary**

**Brief Summary for Lay purposes**: Short description of the primary purpose of the study, including a brief statement of the study hypothesis, intended for the lay public. Ensure that the information provided in the brief summary is consistent with study design, intervention description and study outcomes provided in the form.

This study is a one-arm pre-post test evaluation of a schools-based mental health service. The service, titled Smooth Sailing, is designed to screen and assess the levels of depression and anxiety among secondary high school students. Using an online platform, students register to the service which assesses their mental health symptoms using brief, clinically validated questionnaires. The online platform then allocates each student to one of five "steps" for which different online activities are prescribed. The school counsellor is notified when students are found to be at the severe steps. This 6-week study aims to examine the effects of this service on help-seeking attitudes and behaviour, with secondary analyses on depression and anxiety symptoms, as well as overall acceptability of the service among students. It is hypothesised that improvements in help-seeking attitudes and behaviours will be found, with small effects on depression and anxiety symptoms.

[figure not shown]
# **Background**

Anxiety, depression, and suicidality are prevalent among high school youth aged 12 – 17 years (Lawrence, et al, 2015). Currently, 25% of adolescents are likely to experience a mental health problem, with 1 in 8 reporting an anxiety disorder, and 1 in 16 reporting major depression. Help-seeking is low, particularly amongst males. When help-seeking does occur, finding the "right" type of help can be difficult and current mental health services for this age group are overburdened and lack capacity for mild-moderate symptoms (McGorry, et al. 2013). Alternative service models are needed to improve rates of help-seeking, reduce pressure on current systems, to prevent escalation of mental illness, and reduce the associated morbidity and mortality. It is estimated that prevention and early intervention efforts can reduce rates of mental illness by 20%.

Online stepped-care presents a viable alternative. It is based on the premise that simple, cost-effective internet interventions are offered to youth with mild-moderate symptoms, while more costly, intensive face-to-face interventions are reserved for those with more severe and persistent symptoms (van Straten, et al. 2015). Although complex, this approach is efficient, provides tailored help as required, and can prevent mental illness by detecting symptoms early. Internet interventions can be readily integrated into stepped-care as they are fully automated, acceptable to youth, preserve fidelity of care, and allow for ongoing monitoring and automated feedback. These systems can be engineered to "reach out" to youth rather than wait for them to approach.

School is an ideal setting for the implementation of online stepped-care as students spend much of their daily lives in school, and it is a place of learning new skills and knowledge (Clayton, et al. 2010). However, schools currently have a "scattergun" approach to mental health, with some offering a school counsellor, some offering psycho-education programs, and others not having anything at all. To improve this situation, the Black Dog Institute has been awarded funds (\$517 000) to design, build, and evaluate an online mental health clinic (referred to hereon in as "the e-clinic") that targets help-seeking for depression and anxiety symptoms in high school students. Co-designed with students/schools/parents, the e-clinic delivers mental healthcare using a sophisticated internet program that triages students' mental health, delivers treatment, monitors progress and links in with the school counsellor and wellbeing team. To reduce the stigma associated with mental illness, this e-clinic service has been named "Smooth Sailing".

The theory of change underpinning Smooth Sailing is based on Rickwood et al's (2005) "Help-Seeking model" in which help-seeking is defined as an intensely personal process with four key stages:

Smooth Sailing targets these stages directly by: i) Multiple pathways of entry to satisfy both internal and external awareness and appraisal; ii) Psychometric online screening with feedback; iii) Personalised program of care delivered utilising the stepped care model linking in with face-to-face services and e-support; iv) Training and skill development in disclosure, identifying trustworthy adults at home and at school, knowledge on how to start conversations about mental health and what to do if not wanting to disclose. Smooth Sailing can be described as a "complex intervention" – an intervention with several interacting components. These types of interventions present a number of unique problems for researchers, due to the difficulty in standardising the design and delivery of the intervention, their sensitivity to features of the local context (in this case, the school setting), the organisational and logistical difficulty of applying experimental methods to service design change, and the length and complexity of the causal chains linking the intervention with outcome. As such, the current study aims to evaluate the safety and efficacy (including the acceptability and feasibility) of Smooth Sailing.

# **Trial Objectives and Purpose**

The main objectives of this trial are to:

- Evaluate the effectiveness of Smooth Sailing intervention for increasing help-seeking for depression and anxiety among high school students;
- Measure the acceptability, feasibility, and demand of this type of service model in high school settings.

# **Trial Design**

## **Study Type**

An uncontrolled, non-randomised, one arm pre-post interventional trial.

## **Assignment**

Single Group such that all participants receive the same intervention throughout the study.

## Masking/Blinding of Participants.

This study will be "open" (i.e. masking not used) such that all involved in the study (participant, clinician, and data analyst) are not blinded.

#### **Phase**

Not applicable.

## **Type of Endpoint**

Efficacy/Safety: to measure the intervention's influence on help-seeking for depression, anxiety and stress; and to show that the intervention is safe under conditions of the proposed protocol.

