Step 4	Severe	Self-directed online cognitive behavioural therapy (CBT) in addition to the online psycho-education material and additional support from the school counsellor. In the current study, any participant who reports moderate symptoms will trigger an electronic notification alert which will be automatically sent to the school counsellor or head teacher for further investigation. This will allow the school counsellor to facilitate a face-to-face session to provide the counselling or refer on to external services. It is estimated that 5% of participants will be allocated to this step at baseline.

Throughout the trial, the school counsellor will be physically located within the school that the participant attends. He or she has a background in counselling or psychology and is present at the school at least two days per week. The school counsellor will provide clinical support to any participant that reports moderately severe or severe depression/anxiety scores, or reports suicidal ideation throughout the study. See Assessment of Efficacy for details on how service use, adherence, and satisfaction will be measured.

Table 3. Step Allocations at Day 43 based on Step at Baseline

	Step at Baseline	1	2	3	4
Step at 43 days					
1		1	2	3	4
2		2	3	3	4
3		3	3	4	4
4		4	4	4	4

Comparator: No control group as it is an uncontrolled trial.

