## **Summary of Potential Adverse Events**

The table below outlines a series of possible adverse events that may be captured by the assessments within this study. These events will be monitored by the number of email triggers sent by the service during the study period.

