# **Statistics**

Although this study is an uncontrolled acceptability trial, we will be examining differences pre and post-test. A recent systematic review of help-seeking interventions (Gulliver et al 2012) reports an effect size of d = 0.12 - 0.53 for psycho-education interventions. As such, our sample size calculations are based on using an alpha of 0.05 and effect size of 0.50. As guided by Cohen (1992), 64 participants are needed to demonstrate this effect. Given that 40% are likely to drop out, we will target 106 participants for recruitment.

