#### **Analysis**

Data will be collected using the Black Dog Institute e-health platform. Participant data will then be exported to SPSS statistical software for analyses. Statistical analyses will be performed using SPSS 21.0 (SPSS Inc., Chicago, II, USA). The primary outcome measures will be analysed using mixed modelling which is similar to repeated-measures analysis. This type of analysis will determine any significant differences in the scores reported at time 1 (pre) and then at time 2 (post). The primary hypothesis will be evaluated by differences in pre and post scores on help-seeking questionnaires. Secondary hypotheses will be evaluated by descriptive analyses of the acceptability and feasibility questionnaires.

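### The stated safety aim is to show that Smooth Sailing is safe, but one uncontrolled arm followed to Day 43 can only describe harms

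*Protocol*

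**What the plan says.** The Type of Endpoint section gives two aims. The efficacy aim is to measure influence on help-seeking. The safety aim reads "and to show that the intervention is safe under conditions of the proposed protocol". The Background is more cautious: "the current study aims to evaluate the safety and efficacy (including the acceptability and feasibility) of Smooth Sailing".

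The design is "An uncontrolled, non-randomised, one arm pre-post interventional trial", and the comparator line of the Intervention section confirms this: "No control group as it is an uncontrolled trial". Final measures are taken at Day 43 (Trial Procedure).

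The size rests on the pre-post help-seeking effect alone: "our sample size calculations are based on using an alpha of 0.05 and effect size of 0.50". This gives 64 participants, and then "Given that 40% are likely to drop out, we will target 106 participants for recruitment".

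On harms, the Summary of Potential Adverse Events says "These events will be monitored by the number of email triggers sent by the service during the study period". The table that follows lists three events identified by questionnaire score (PHQ-9 of 15 or above, GAD-7 of 15 or above, any positive answer to PHQ-9 item 9). All three are labelled as baseline events. A second table covers events that school counsellors report, and the trial manager asks counsellors about adverse events at the 6-week follow-up. The section on responding to risk of significant harm also triggers alerts from follow-up scores, but the event table does not list these as events.

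**The concern.** To show safety, a trial needs something to show it against: a comparator, a reference rate, or a limit that the harm rate must stay below. The protocol gives none of these, and safety does not appear among the hypotheses. If no harm were seen, the data would still allow a harm rate that may matter in this population, which is aged 12 to 19 and includes students with current suicidality (Inclusion Criteria). If harms were seen, they could not be separated from the natural course of symptoms over six weeks.

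The metric adds to the problem. A score recorded at registration, before the student has received any content, says nothing about harm from the intervention. A running total of emails also has no denominator, and the protocol does not say whether a student who meets several criteria generates one trigger or several.

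**Working it through.** **Inputs.** Evaluable 64, recruited 106, dropout 40%, alpha 0.05, effect size 0.50 (Statistics). Final assessment at Day 43 (Trial Procedure). No harm rate or margin is stated anywhere, so zero observed events is taken as the most favourable case.

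**The plan's own figures.** For two independent means with d = 0.50, two-sided alpha 0.05 and 80% power (assumed, since power is not stated), the t-test calculation gives 63.8, so 64 per group. Dropout: 64 / (1 − 0.40) = 106.7. The stated 106 agrees apart from rounding down. No safety quantity enters this calculation.

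**Upper limit with zero events in n students (exact binomial).** One-sided 95%: 1 − 0.05^(1/n). Upper end of the two-sided 95% interval: 1 − 0.025^(1/n). Check: 3/n.

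| Students observed | One-sided | Two-sided | 3/n |
|---|---|---|---|
| 106 (all recruits) | 1 − 0.05^(1/106) = 2.8% | 1 − 0.025^(1/106) = 3.4% | 2.8% |
| 64 (expected at Day 43) | 1 − 0.05^(1/64) = 4.6% | 1 − 0.025^(1/64) = 5.6% | 4.7% |

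The first row applies to harms that counsellors could report for any registered student. The second applies to harms seen only in the Day 43 questionnaires, which can be completed only in the supervised class session.

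**Chance of seeing at least one case**, 1 − (1 − p)^n. The rates p are illustrative.

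| True rate | n = 64 | n = 106 |
|---|---|---|
| 1% | 47% | 66% |
| 2% | 73% | 88% |

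A harm that affects 1 student in 100 would therefore go unseen with probability 53% in 64 students and 34% in 106.

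**What the trigger count would contain.** The care table expects 10–15% of students at Step 3 and 5% at Step 4 at baseline, so 15–20% in total. Those steps meet the score criteria for an alert. Of 106 students that is 0.15 × 106 = 15.9 to 0.20 × 106 = 21.2, or about 16 to 21 students with baseline triggers before any alert for suicidal ideation is added. The total is filled in advance by events that precede exposure. It would be well above zero for an intervention that does no harm, and it would not isolate the alerts and reports that arise later.

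**The case against.** The strongest reply is that the line under Type of Endpoint is a short descriptor in a run of form-like fields. The main objectives name effectiveness, acceptability, feasibility and demand. No safety hypothesis is set, the Statistics section calls the study an acceptability trial, and the Background only speaks of evaluating safety. This stands as a reason to rate the point low. It does not remove it, because the sentence states an aim that the other sections neither share nor support.

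A reader might go further in four ways that the protocol does not support.

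- *That no safety analysis is planned.* The Analysis section's secondary provision is "Secondary hypotheses will be evaluated by descriptive analyses of the acceptability and feasibility questionnaires", which leaves safety out. But a statistical analysis plan that is not shown may supply one, and safety monitoring is described at length. No analysis plan, however, can add a comparator or longer follow-up.
- *That the trial leaves a harm rate of 5–6% open, without qualification.* The 5.6% figure is two-sided and applies to the 64 expected at Day 43. Counsellor reports can cover all 106, which gives 2.8% or 3.4%.
- *That few events will be reported as proof of safety.* No section says so. The publication policy promises only that results will be reported.
- *That up to 40% of recruits might have been harmed unseen.* This bound assumes that every student without Day 43 data was harmed. It is arithmetically possible but uninformative.

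It is also fair to say that zero events is not what the protocol predicts for its listed baseline events. The limits above concern harms that arise after registration.

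**Conclusion.** The point holds as a mismatch between a stated aim and what the design can deliver, and it is minor. With one uncontrolled arm and no threshold or reference rate, the trial can describe harms up to Day 43 but cannot demonstrate safety. Even with no event, the upper 95% limit is 2.8% one-sided (3.4% two-sided) with all 106 students covered, and 4.6% (5.6%) with 64. A count of email triggers cannot carry the aim either, because the events defined by score are baseline states and the count is not a proportion of students.

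The limits assume that 106 are recruited, that 40% are lost as planned and that students are independent. Recruitment is by class group of about 30, so any clustering would widen them. The 106-student figures also assume that counsellor reporting reaches students who miss the Day 43 session. The sample size and the efficacy analysis are unaffected.

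**What to change.** 1. Under Type of Endpoint, replace the aim of showing safety with: to describe the frequency of harms arising after registration. This brings the section into line with the Background.
2. Report, separately from baseline alerts, the number of students with a post-registration event over the number observed, with an exact 95% confidence interval. Post-registration events are follow-up alerts and counsellor reports. Give each source its own denominator: students who completed the Day 43 questionnaires for follow-up alerts, and registered students covered by counsellor enquiry for the reports.
3. State that absence of events will not be reported as evidence of safety.

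The cost is a less favourable stated aim and one small table from data already collected. No additional students, assessments or changes to the alert procedure are needed.

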## **Inclusion Criteria**

Participants will be aged between 12 – 19 years and attending one of the participating high schools. Both males and females will be eligible. As well as including participants that are well, this trial will include adolescents with current depressive symptoms or any adolescents with a history of depression or anxiety. This trial will also include adolescents with current suicidality or a history of suicidality. Participants will be required to have an active email address for the duration of the trial as well as internet access either at home or at school (the school will provide internet access for the duration of the trial). Only those who provide signed written consent from their parents will be included.

#### **Exclusion criteria**

Those not willing or able to provide individual and parental consent will be excluded from participating.

#### **Hypotheses**

Those who participate in the intervention will report improvements in help-seeking, mental health knowledge, greater satisfaction with school care, and lower levels of depression and anxiety.

# **Selection and Withdrawal of Subjects**

## **Recruitment, Screening & Consenting**

Status: Completed

Potential participants will be identified from the high schools who consent to participating in the trial. High schools will be recruited from a shortlist of schools that have established research and educational partnerships with the Institute. This list consists of approximately 20 local and regional high schools that have previously participated in a trial or have expressed interest in participating in a research trial. These schools are based in NSW only and their postcodes include 2440 (Kempsey, NSW), 2290 (Charlestown, NSW), 2131 – 2372 (Canterbury /Bankstown), 2008 – 2036 (Eastern Suburbs), 2006 – 2372 (Inner West), 2163 – 2566 (Liverpool /Fairfield), 2020 – 2223 (St George), 2173 – 2565 (Sutherland), 2145 – 2770 (Western Sydney), 2115 – 2199 (Parramatta).

Schools are initially emailed a study invitation from the chief investigator using a standard letter attachment. This email consists of an overview of the study, and a brief protocol (adapted from this document). The schools are invited to participate in a follow-up phone call to answer any additional questions. Once this is complete, consenting schools are asked to sign and date a letter of support which is then returned to the Chief Investigator. This is then forwarded to the governing ethics bodies. Once a school's participation has been secured, the school counsellor is briefed on the study and the study protocol is explained by the trial manager. The school then selects a class group of approximately 30 students based on teacher co-operation and general study suitability (e.g., in terms of school demands such as exams, curriculum studies, other research study participation). Due to the inclusion/exclusion criteria, there is no need for screening of these participants. Once the class is selected, one or more members of the research team will visit the school during the first two weeks of the school term to oversee the baseline assessment. Participant Information and Consent will be disseminated ahead of this time via mail, so that students have adequate time to seek parental consent before the baseline assessments. To avoid coercion, students are asked to sign their forms outside of school time. Final participants are those who return their personal consent forms along with parental permission.

#### Withdrawal

The Participant Information Statement and Consent Form informs potential participants that participation is completely voluntary, and that they are free to withdraw from the study at any time, without penalty and without having to give a reason. The Parent/Guardian Information Statement and Consent Form also informs parents/guardians that participation is completely voluntary, and that they are free to withdraw their consent and/or permission for their child to participate at any time, without penalty and without having to give a reason. Participants wishing to withdraw from the study can do so by contacting the trial manager and providing either their first name and last name, or unique ID code. No reasons need to be given.

# **Trial Procedure**

Once parental consent is collected, the research team will visit the school to supervise participants' registration to the intervention (i.e. day one). The registration process will be completed online, during class time, using a computer/mobile/ or tablet device. Registration is estimated to take no more than 20-30 minutes. Although registration is completed privately by the student, a researcher or trained school staff member will be present to answer any questions and offer assistance. Baseline measures will be collected during this online registration process. Once all students have registered and completed the baseline assessment, a list of student names, alongside their trial identification numbers, will be given to the school counsellor. This will be used when the school counsellor is required to follow-up with a student as the email alerts do not contain student names (only the trial identification numbers). Throughout the trial, students will be able to use the intervention at their own leisure, either in or out of school time. Participants will also receive two optional monitoring questionnaires which are delivered via email (with SMS reminder) at day 15 and day 29. At day 43, a researcher will return to the school to collect the final endpoint measures using the same procedure for registration.

# **Treatment of Subjects**

#### Intervention

**Name**: Smooth Sailing (Arm 1). Intervention codes: Early detection/screening and Treatment (other) (behavioural intervention)

Smooth Sailing is an online mental health service designed and administered by the Black Dog Institute. It is based on the principles of "stepped care" such that the intensity of the recommended interventions is matched to individuals' symptom severity and individuals "step up" if they have not responded to treatment after a set period of time. Exposure to Smooth Sailing involves:

- 1. Registration & Mental Health Assessment. In class time, participants are given a slip of paper with the service URL and their unique identification code. They then use a school or personal internet device to visit this website and undertake registration. Before registration commences, participants are asked to complete the Gillick Competency measure which consists of X questions to further confirm their understanding of the service and study requirements. Upon correct completion of this, participants are invited to create a personal profile (name, date of birth, email address, mobile phone number, and gender, history of mental health issues, and use of the internet for mental health information). Once a personal profile is created, four questionnaires were used to measure the presence of depression, anxiety, help-seeking attitudes and behaviours (see Appendix B in Attachments section of ANZCTR record). This takes approximately 30 minutes to complete.
- 2. Step allocation. Based on the answers inputted during registration, Smooth Sailing allocates each participant to one of five "steps". This is automatic and based on a clinical algorithm which accounts for the severity levels of the anxiety and depression symptoms as reported by the participant on the Generalised Anxiety Disorder Scale (GAD-7) and the Patient Health Questionnaire (PHQ-9). Each "step" matches a severity level and was based on clinical practice guidelines. The step allocations were: Nil/minimal (Step 0), Mild (Step 1),

Moderate (Step 2), Moderately Severe (Step 3), and Severe (Step 4). Please see Table 1 for more detail.

- 3. Delivery of tailored program. After step allocation, Smooth Sailing delivers a program of content that is tailored to each step. Steps 0 and 1 receive online psychoeducation. Step 2 receive online psychoeducation + online self-directed Cognitive Behavioural Therapy (CBT). Steps 3 and 4 receive online psychoeducation + online self-directed CBT + additional support from the School Counsellor. Any participant who was allocated to Step 3 or 4 triggered an electronic notification alert which was automatically sent to the school counsellor for further investigation. This allowed the school counsellor to facilitate a face-to-face session within 48 hours to provide the counselling or refer on to external services. The online psychoeducation consists of five modules on i) general mental health, ii) depression, iii) anxiety, iiii) seeking help for yourself, iv) seeking help for a friend. Each of these modules contains information about definitions of mental health terms, signs and symptoms, causes of mental health problems, what to do if needing help, and strategies and tips for what a young person can do immediately. Each module is complemented by animations and illustrations to depict key messages as well as hyperlinks to other credible youth mental health services and websites including Headspace, Reachout, Kids Helpline. This content was created specifically for this service, and was reviewed by clinicians. It is designed to be self-directed, such that the youth can read and return to it whenever they wish. The online CBT module consists of a single webpage that outlines two evidence-based self-directed online cognitive behavioural therapy programs: i) MoodGym (Australian National University) and ii) Brave Online (University of Queensland). MoodGym is an interactive self-help book which helps to learn and practise skills for managing symptoms of depression and anxiety. It consists of five modules alongside questionnaires, summaries and a personal workbook. BRAVE was developed for children and teenagers who experience Separation Anxiety Disorder, Social Phobia, Specific Phobia and Generalised Anxiety Disorder. This program helps young people to learn new ways to manage their anxiety and fears. It consists of 10 sessions and is effective for reducing social worries, anxiety about separating from loved ones, fears of specific objects or situation, worries about friendships, school performance or other everyday worries. Please see Table 2 for more detail.
- 4. Monitoring and Feedback. At two points in the study (Day 15 and Day 22) participants received an automated 18-item "monitoring questionnaire" to assess how they were doing. This consisted of the Goldberg Depression and Anxiety Scales and was delivered via email or SMS. An automated thank you message was received alongside a reminder to use the program if participants completed this questionnaire.
- 5. Reassessment (Post-test/endpoint): At Day 43, researchers revisited the schools. Participants again logged onto the service using the same URL and unique ID codes and were delivered the final endpoint questionnaires. In theory, the results of these questionnaires would be used to determine whether a participant had responded to care or needed to be "stepped up". In accordance with the Clinical Practice Guidelines for the Treatment of Depression in Young Adults, if a participant has not responded to their care within 43 days of their baseline allocation, they would be "stepped up" to the next level of care. See Table 3 below for the stepping matrix at 43 days. The matrix was designed such that a participant would not be stepped down, instead will either remain at the same step or step up. However, as the current trial ceased at 43 days, no stepping occurred during this trial. Instead, this trial was

designed to provide the clinical data necessary to determine whether the steps are feasible for future trials.

Throughout the trial, participants will be obligated to use Smooth Sailing at pre-test (for registration and baseline measure collection) and again at post-test (for reassessment and final endpoint collection) only. Completion of the monitoring questionnaires and use of the other components is entirely voluntary, and will be a measured as part of the study.

